2.2 BACKGROUND

In collaboration with a media services company (Triad Interactive Media, Greensboro, NC), we developed a radon app for smartphones.¹¹ Briefly, the app uses a framework in HTML5 and the open source Twitter API. Posts created by the app are cross-listed on Twitter. Once users log in via Twitter, they can view radon news and mobile-friendly informative content on radon repurposed from EPA brochures. Users also can access existing Tweets containing hashtags, e.g., #radon, #radonawareness, #radonmitigation, and #lungcancer. Individual users' activities on the radon app, along with their Twitter handle, are saved on Triad Interactive Media's server. Through the app, users could order a free radon test kit at any time.

We conducted a pilot clinical trial using this app. Ninety six (96) undergraduates at the University of North Dakota in Grand Forks, ND (UND) were assigned to use the radon app for one month and were tested on several aspects of radon knowledge and testing using a pretest-posttest design.¹¹ We have recently published our findings.¹¹ We found that the use of the radon app: (1) significantly improved individuals' radon knowledge and generated positive attitudes toward radon testing; (2) significantly increased self-efficacy (i.e., an individual's perceived capability to order a radon test kit and use it); (3) significantly increased response efficacy (i.e., an individual's evaluation of the effectiveness of radon testing in preventing radon exposure); and (4) resulted in 24% of study participants ordering a free radon test kit. However, only a small percentage of participants actually used the test kit they obtained (i.e., employed the test in their home and returned it to the lab; a total test completion rate of 9%).

In summary, our pilot trial demonstrated that the radon app improved radon knowledge, motivation to test, and stimulated requests for free test kits. However, our pilot trial had a key limitation: there was no control group (i.e., a group not exposed to the app). Our present research builds and improves upon these preliminary findings. To do so, we will include a control group that receives usual care (radon information communicated via EPA brochures).

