4 STUDY DESIGN

4.1 OVERALL DESIGN

The project begins by comparing the role of the radon app vs. brochures on the percentage of participants that request free test kits and use and return them to the laboratory for analysis and improving knowledge about radon (Phase II).

Experimental design. We designed an online experiment with two experimental conditions—the radon app condition vs. brochure condition—using a pretest-posttest design. Study participants are undergraduates in the Communication Department at UND, indicating that this is a single-site trial. The principal eligibility criterion is that participants own a smartphone. The principal exclusion criterion is previous testing for radon within the past two years.

We consider UND undergraduates to be an appropriate population to test the app for several reasons: (1) ND has the highest residential radon levels in the U.S.²; (2) Our recent review of radon knowledge indicated that most individuals less than 30 years old do not know what radon is¹²; and (3) The age of many undergraduate students is similar to that of first time home-buyers in the U.S.¹³ We will assign recruited participants randomly to one of the two experimental conditions: app use and brochures.

Participants in both experimental conditions will complete an online pre-exposure survey during the baseline phase of the study. Upon completion of the pre-exposure survey, participants assigned to **the radon app condition** will be asked to install the radon app on their smartphones and use the app for three months. App installation will be verified electronically via text message sent to the investigators. To make the informational content of the radon app and EPA brochures equivalent, the informational content in the app condition will be repurposed from EPA brochures used in the brochure condition. Participants in the radon app condition will have the opportunity to order a free radon test kit through the app at any time during the three-month period.

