completing the pre-exposure survey. Once the app is installed in participants' own phones and they successfully log in through their Twitter credentials, they will be asked to keep the app on their phone for three months with the notification setting "on". After all these steps are completed, they will be asked to complete the pre-exposure survey. The radon app can be accessed via computer or smartphone: <https://radon-production.herokuapp.com/>

The other half of the participants assigned to the brochure condition will be asked to provide the mailing address prior to completing the pre-exposure survey so that they can receive EPA brochures in the next 3 months via postal mail. Once this step is completed, they will be asked to complete the pre-exposure survey. During the 3-month period, participants assigned to the radon app condition will receive the radon educational materials via the app. Materials include the informational content repurposed from EPA brochures and radon-education Tweets using hashtags, such as #radon, #lungcancer, #healthylungs, and #radonawareness. The app uses the Twitter's mechanism so that's why participants need to use their Twitter credentials to login, and those hashtags used in Tweets are automatically detected by the app, and will be populated in the app. While keeping the app for three months, if participants would like to test their homes for radon levels, as education materials they will be exposed to encourage to do so, they can request a free radon kit through the app. They will be asked to enter their mailing address, email, and phone number so that the kit will be delivered to their home address. Although the app would collect such personal information, this is only to provide them with the free radon kit, and such information won't be attached to their any survey responses. On the other hand, participants assigned to the brochure condition will receive a total of three EPA brochures, with each one being delivered once a month. In each mailing, participants will receive a pre-addressed, pre-paid postcard to request a free radon test kit. The postcard will be addressed to a UND address so that we can track the number requested by participants in the brochure condition.

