8 STUDY ASSESSMENTS AND PROCEDURES

8.1 ENDPOINT AND OTHER NON-SAFETY ASSESSMENTS

Once a participant will be directed to the Qualtrics pre-exposure survey link, the consent form will appear on the first page of the survey. Participants will be asked to read it and proceed if they agree. All participants will be asked to answer pre-exposure survey questions measuring key variables, such as radon knowledge, and demographic information to be used in the analyses (e.g., age, gender, home-owner status, smoking status). They will then be randomly assigned to one of the two conditions (via Qualtrics survey's randomization function). Participants assigned to the radon app condition will receive instructions on how to install the app and be instructed to use the app for the next three months. On the other hand, participants assigned to the brochure condition will receive appropriate instructions and be asked to submit both their mailing and email addresses so that they can receive three brochures in the next three months and be contacted for the post-exposure survey. Next, Participants' email and mailing addresses will not be attached to their responses to the pre-exposure survey to protect participants' privacy and confidentiality. Once participants complete the pre-survey, we have the data telling us that: which email address was assigned to which condition, and the timing. After 3 months, we will send the post-exposure survey link to that email address individually. Participants' behaviors,

which are two primary endpoints (i.e., test kit ordering and utilizing behaviors) will be recorded as they become available during the 3-month period.

In summary, participants in both experimental conditions will complete an online pre-exposure survey during the baseline phase of the study and then are randomized to the app or the brochure group. The experimental groups differ only in the means by which information is conveyed, not in the nature of the information. Participants in both conditions will have the opportunity to order a free radon test kit at any time during the three-month period.

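### Section 8.1 says the arms differ only in medium, but the app adds Tweets, notifications and in-app ordering, so a kit difference belongs to the whole package

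*Combined protocol and SAP*

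**What the plan says.** Section 8.1 summarises the contrast in one sentence: "The experimental groups differ only in the means by which information is conveyed, not in the nature of the information". The basis is given in section 4.1 and repeated in the synopsis (1.1) and in 6.1.1 and 6.1.2: the content is made equivalent because "the informational content in the app condition will be repurposed from EPA brochures used in the brochure condition".

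Section 5.5 then lists what app participants receive in this trial: "Materials include the informational content repurposed from EPA brochures and radon-education Tweets using hashtags, such as #radon, #lungcancer, #healthylungs, and #radonawareness". The same section has the app pick up those hashtagged Tweets automatically and asks participants to leave notifications on for three months. Brochure participants receive three EPA brochures, one a month.

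Kits are requested by different routes. App participants order inside the app. For the brochure arm, "In each mailing, participants will receive a pre-addressed, pre-paid postcard to request a free radon test kit". Section 8.1 nevertheless says: "Participants in both conditions will have the opportunity to order a free radon test kit at any time during the three-month period".

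The primary objective (1.1 and section 3) concerns the effectiveness of radon information by app or by brochure, judged on ordering and returning kits. Section 4.2 describes the trial more broadly, as a smartphone app against usual care.

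**The concern.** If the arms really differed only in medium, a higher request rate with the app would show that the same information works better on a phone than on paper. That is the natural reading of the primary objective together with section 8.1. Three features of the app arm break it: added content (Tweets), prompts (notifications), and a different way of placing the order. The third matters because the first primary endpoint counts kit requests, so the ordering route is part of how the outcome is produced. The second, kits used and returned, follows from the first. A difference could come from any of these features even if the medium itself changed nobody's motivation to test.

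At stake is what the trial may conclude. The validity of the randomised test is not in question.

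**Working it through.** **Step 1: the sections side by side.**

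| Feature | App arm | Brochure arm | Consistent with the 8.1 claim? |
|---|---|---|---|
| EPA content | Repurposed from the brochures (4.1) | The brochures (4.1) | Yes |
| Tweets | Yes, by hashtag (5.5) | None described | No: extra information |
| Prompts | Notifications on (5.5) | Three monthly mailings (5.5) | A difference beyond content |
| Kit request | Inside the app (4.1, 5.5) | Pre-paid postcard in each mailing (5.5) | Not about information, but feeds the endpoint |
| When a request is possible | Any time (4.1) | As described, once the first postcard has arrived | Conflicts with the ordering sentence in 8.1 |

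The Tweets contradict the statement about the nature of the information directly. The ordering route does not contradict that sentence, but it prevents a kit difference from being read as an effect of information delivery.

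**Step 2: does the analysis separate these parts?** Section 9.4.2 specifies a directional Z test for two proportions. Section 9.4.7 adds regression with participant characteristics and time spent using the app. Neither separates content, prompts or ordering route from medium. With two arms that differ in all of them, no analysis of arm differences alone could.

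**Step 3: a hypothetical size for the ordering route.** The plan gives no figure to reproduce here. Inputs:
- n = 100 per arm (9.2).
- Intention to order q = 0.24 in both arms. This borrows the pilot's one-month app ordering rate (2.2); treating it as intention is an assumption.
- Postcard completion m = 1.0, 0.9, 0.8, 0.7. Assumed; the documents give no figure.
- One-sided alpha 5%, and 2.5% for comparison. Assumed; the plan says directional but states no level.

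Ordering probabilities are q in the app arm and q × m in the brochure arm:
- m = 1.0: 24.0% v 24.0%, difference 0
- m = 0.9: 24.0% v 21.6%, difference 2.4 points
- m = 0.8: 24.0% v 19.2%, difference 4.8 points
- m = 0.7: 24.0% v 16.8%, difference 7.2 points

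With a and b the numbers ordering and p = (a + b)/200, z = (a − b)/100 ÷ √[2p(1 − p)/100]. The chance of a significant result is the sum of Bin(a; 100, q) × Bin(b; 100, qm) over all pairs with z above 1.645 (or 1.960).

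| m | One-sided 5% | One-sided 2.5% |
|---|---|---|
| 1.0 | 0.050 | 0.025 |
| 0.9 | 0.108 | 0.060 |
| 0.8 | 0.206 | 0.129 |
| 0.7 | 0.351 | 0.246 |

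For kits used and returned, starting instead from the pilot's 9% completion rate (2.2), the one-sided 5% results for m = 0.9, 0.8, 0.7 are 0.08, 0.12 and 0.18.

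**Step 4: the opposite direction.** Friction may also fall on the app arm. Section 5.5 requires a Twitter login, with a new account if needed, and entry of address, email and phone number to order. Swapping the arms in Step 3 (q × 0.9, 0.8 or 0.7 in the app arm, q in the brochure arm) gives 0.020, 0.007 and 0.002 at one-sided 5%. Step 3 therefore shows what one assumed direction would do; it is not an estimate of bias.

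**The case against.** The strongest reply is that the package contrast is already in the plan. Section 4.2 compares the app with usual care, section 2.2 calls the control usual care, and both ordering routes are described openly. This stands, and it limits the point to the places that claim more: the 8.1 sentence, the equivalence statements and the wording of the primary objective.

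A reader might infer more in four places, and the documents do not support it.

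- *That ordering route confounds the primary comparison.* Both routes are assigned by randomisation as parts of the interventions. The Z test is valid for app against brochure as delivered; only attribution to a single component is limited.
- *That 11/21/35% are false-positive rates.* Under the app v usual care contrast they are the power to detect a real difference in orders. They mislead only if the result is then described as an effect of medium.
- *That radon news is a further difference in content.* It appears in the section 2.2 description of the app, where users "they can view radon news and mobile-friendly informative content on radon repurposed from EPA brochures". The section 5.5 list for this trial does not mention it, and the point does not need it.
- *That the brochure arm is seriously restricted in when it can order.* The first mailing is not dated, the schedule (1.3) starts both interventions on Day 1, and the postcards carry no stated expiry. App users likewise cannot order before installing. The ordering-time sentence is inexact, but the matter is minor.

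The postcard is also pre-addressed, pre-paid and sent three times. That lowers its burden without making the two routes the same.

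**Conclusion.** The point holds as one of description and interpretation. The statement in 8.1 and the equivalence statements in 1.1, 4.1, 6.1.1 and 6.1.2 cannot stand beside section 5.5, which gives the app arm Tweets as well as the EPA content, with notifications on, and a different way to request a kit. The randomised comparison is sound for the package. A difference in kits requested or returned cannot be attributed to the delivery medium of the same information.

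The conclusion about wording rests on the text alone and needs no assumption. The size is hypothetical: 5/11/21/35% at one-sided 5% and 2.5/6/13/25% at one-sided 2.5%, for assumed postcard completion of 100/90/80/70%, equal 24% intention and 100 per arm. The net direction of ordering friction is unknown.

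**What to change.** 1. Replace the 8.1 sentence, and the equivalence statements in 1.1, 4.1, 6.1.1 and 6.1.2, with a package contrast: the app with EPA content, Tweets, notifications and in-app ordering, against mailed EPA brochures with a postcard in each mailing.
2. Reword the primary objective in 1.1 and section 3 to match the app v usual care framing in 4.2.
3. In 8.1, correct the ordering statement for the brochure arm: a kit can be requested from receipt of the first postcard.
4. State that conclusions on kits requested and kits returned apply to the package and are not evidence about medium alone.

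These are text changes. They need no new data and leave the interventions and the primary test as they are. The cost is a narrower claim: the trial could report that the app package did better or worse than mailed brochures, but not that the same information works better on a phone.

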8.2 SAFETY ASSESSMENTS

N/A

8.3 ADVERSE EVENTS AND SERIOUS ADVERSE EVENTS

N/A

8.4 UNANTICIPATED PROBLEMS

8.4.1 DEFINITION OF UNANTICIPATED PROBLEMS

This protocol uses the definition of Unanticipated Problems as defined by the Office for Human Research Protections (OHRP). OHRP considers unanticipated problems involving risks to participants or others to include, in general, any incident, experience, or outcome that meets **all** of the following criteria:

- Unexpected in terms of nature, severity, or frequency given (a) the research procedures that are described in the protocol-related documents, such as the Institutional Review Board (IRB)-approved research protocol and informed consent document; and (b) the characteristics of the participant population being studied;
- Related or possibly related to participation in the research (“possibly related” means there is a reasonable possibility that the incident, experience, or outcome may have been caused by the procedures involved in the research); and
- Suggests that the research places participants or others at a greater risk of harm (including physical, psychological, economic, or social harm) than was previously known or recognized.

8.4.2 UNANTICIPATED PROBLEMS REPORTING

The PI will report unanticipated problems (UPs) to the reviewing Institutional Review Board (IRB). The UP report will include the following information:

- Protocol identifying information: protocol title and number, PI’s name, and the IRB project number
- A detailed description of the event, incident, experience, or outcome.

- An explanation of the basis for determining that the event, incident, experience, or outcome represents an UP.
- A description of any changes to the protocol or other corrective actions that have been taken or are proposed in response to the UP.

To satisfy the requirement for prompt reporting, UPs will be reported using the following timeline:

- UPs that are serious adverse events (SAEs) will be reported to the IRB within 14 working days of the investigator becoming aware of the event.
- Any other UP will be reported to the IRB within 14 working days of the investigator becoming aware of the problem.
- All UPs should be reported to appropriate institutional officials (as required by an institution's written reporting procedures), the supporting agency head (or designee), and the Office for Human Research Protections (OHRP) within 14 working days of the IRB's receipt of the report of the problem from the investigator.

8.4.3 REPORTING UNANTICIPATED PROBLEMS TO PARTICIPANTS

N/A

9 STATISTICAL CONSIDERATIONS

9.1 STATISTICAL HYPOTHESES

- Primary Endpoint(s): **H₀**: The incidence of: (a) participants' requests for free radon kits and (b) participants utilizing the test kits and returned to Alpha Energy Labs among those assigned to the radon app condition and those assigned to the brochure condition will not differ. **H₁**: The incidence of: (a) participants' requests for free radon kits and (b) participants utilizing the test kits and returned to Alpha Energy Labs will be higher among those assigned to the radon app than the brochure condition.

H₀: The difference in the incidence of request for and utilization of radon test kits between the radon app and brochure conditions will not be affected by participants' gender, age, race, smoking status, or geographic location (state/county of birth). **H₁**: There is significant interaction between the radon app and brochure conditions and the variables above in terms of the proportion requesting and utilization of test kits.

- Secondary Endpoint(s): **H₀**: There will be no changes in radon knowledge among those assigned to the radon app condition and those assigned to the brochure condition. **H₁**: There will be more positive changes in radon knowledge among participants assigned to the radon app condition.

9.2 SAMPLE SIZE DETERMINATION

Primary endpoints:

1. Number of radon test kits requested by participants in the radon app and brochure conditions; and
2. Number of radon test kits used and returned to the laboratory by participants in the two conditions.

Secondary endpoints:

Effectiveness of the radon app vs. brochure at 3 months re: changes in radon knowledge, as measured by the number of correct responses to a series of 20 true/false questions (e.g., “The EPA recommends that homes with 4 picocuries per liter (pCi/L) or more of radon should be fixed.”).

Sample size determination:

A sample size of at least 100 people in each group will have a power of .8 to .9 to detect differences in proportions of at least 20%, Chi-square values of five or more with one or two degrees of freedom, mean differences of at least 0.3, and odds ratios greater than three in logistic regression.

Statistical analyses:

H₀: The incidence of: (a) participants’ requests for free radon kits and (b) participants utilizing the test kits and returned to Alpha Energy Labs among those assigned to the radon app condition and those assigned to the brochure condition will not differ. **H₁**: The incidence of: (a) participants’ requests for free radon kits and (b) participants utilizing the test kits and returned to Alpha Energy Labs will be higher among those assigned to the radon app than the brochure condition. **Statistical test**: We will use a directional Z test for difference in proportions to determine whether the incidence of requested and returned kits is higher for those assigned to the radon app condition with SAS. Differences will be described using absolute and relative differences in proportions.

H₀: There will be no changes in radon knowledge among those assigned to the radon app condition and those assigned to the brochure condition. **H₁**: There will be more positive changes in radon knowledge among participants assigned to the radon app condition. **Statistical test**: Differences in radon knowledge between the two groups will be tested with directional, independent t-tests, with SAS.

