Participants who completed the pre-exposure survey then received an email reminder including the link for the post-exposure survey three months after the completion of their pre-exposure survey. Participants who did not complete the post-exposure survey two weeks after the initial email received a reminder email.

A sample size of at least 100 students in each group was determined to have a power of .8 to .9 to detect differences in proportions of at least 20%, Chi-square values of five or more with one or two degrees of freedom, mean differences of at least 0.3, and odds ratios greater than three in logistic regression.

Participant incentives:

Students who were enrolled in COMM 110 class received 0.5 extra course credit point for the completion of pre-exposure survey, which was equivalent to the half-hour research participation. If they completed the second and final session (i.e., post-exposure survey), they received additional 0.5 extra credit point.

Students who were enrolled in COMM 102 class met the half-hour research participation requirement for completing the pre-exposure survey. If they completed the second and final session (i.e., post-exposure survey), they met additional half-hour research participation requirement.

In addition to extra credit or meeting the research requirement, students received a \$10 gift card for the completion of pre-exposure survey. If they complete the second and final session (i.e., post-exposure survey), they received another \$15 gift card.

All students included in the Comm department's SONA research pool are 110 and 102 students, and they are taught by GTAs (110) and a designated instructor (102). The PI has never taught 102 or 110 courses, and will not do so. But in case any of PI's students are invited to the study, they will be given an option to complete an alternative task as a way to avoid coercion or undue influence.

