7.3 LOST TO FOLLOW-UP

A participant will be considered lost to follow-up if he or she fails to complete the post-exposure survey and study staff are unable to contact the participant after at least 2 attempts.

The following actions must be taken if a participant fails to complete the post-exposure survey:

- The site will attempt to contact the participant, counsel the participant on the importance of maintaining the assigned visit schedule and ascertain if the participant wishes to and/or should continue in the study.
- Before a participant is deemed lost to follow-up, the investigator or designee will make every effort to regain contact with the participant via a reminder email. These contact attempts will be documented in the participant's medical record or study file.
- Should the participant continue to be unreachable, he or she will be considered to have withdrawn from the study with a primary reason of lost to follow-up.

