9.4.2 ANALYSIS OF THE PRIMARY ENDPOINT(S)

Primary endpoints:

1. Number of radon test kits requested by participants in the radon app and brochure conditions; and
2. Number of radon test kits used and returned to the laboratory by participants in the two conditions.

Ho: The incidence of: (a) participants' requests for free radon kits and (b) participants utilizing the test kits and returned to Alpha Energy Labs among those assigned to the radon app condition and those assigned to the brochure condition will not differ. **H1:** The incidence of: (a) participants' requests for free radon kits and (b) participants utilizing the test kits and returned to Alpha Energy Labs will be higher among those assigned to the radon app than the brochure condition. **Statistical test:** We will use a directional Z test for difference in proportions to determine whether the incidence of requested and returned kits is higher for those assigned to the radon app condition with SAS. Differences will be described using absolute and relative differences in proportions.

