9.4.3 ANALYSIS OF THE SECONDARY ENDPOINT(S)

Secondary endpoints:

Effectiveness of the radon app vs. brochure at 3 months re: changes in radon knowledge, as measured by the number of correct responses to a series of 20 true/false questions (e.g., "The EPA recommends that homes with 4 picocuries per liter (pCi/L) or more of radon should be fixed.").

Radon knowledge will be measured by the number of accurate responses to 20 True-False statements in T1 (baseline) and T2 (at 3 months).¹¹ The response options will be: "true," "false," and "I don't know." Participants' responses to each statement will then be re-coded to 1 ("correct") or 0 ("incorrect" or "I don't know"). After that, two radon knowledge index variables (continuous) will be created by summing participants' responses to each statement in T1 (baseline) and T2 (at 3 months). Lower numbers on index variables indicate a low level of knowledge, whereas higher numbers indicate greater knowledge.

H₀: There will be no changes in radon knowledge among those assigned to the radon app condition and those assigned to the brochure condition. **H₁**: There will be more positive changes in radon knowledge among participants assigned to the radon app condition. **Statistical test**: Differences in radon knowledge between the two groups will be tested with directional, independent t-tests, with SAS.

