9.4.7 SUB-GROUP ANALYSES

Primary endpoints will be analyzed based on gender, age, race, smoking status, or geographic location (state/county of birth):

H₀: The difference in the incidence of request for and utilization of radon test kits between the radon app and brochure conditions will not be affected by participants' gender, age, race, smoking status, or geographic location (state/county of birth). **H₁**: There is significant interaction between the radon app and brochure conditions and the variables above in terms of the proportion requesting and utilization of test kits. **Statistical test**: We will use multivariate regression analyses predicting incidence of requesting and utilization of test, while controlling for gender, age, race, smoking status, location, and time spent using the app with SAS. Interactions will be tested in multivariate models and significant interactions will be described by levels of univariate Z or chi-square tests.

Secondary endpoints will not be analyzed based on gender, age, race, smoking status, or geographic location (state/county of birth).

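### The power statement in 9.2 cannot be verified as written and, at a conventional 5% level, does not hold for all four of its effects

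*Combined protocol and SAP*

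**What the plan says.** The plan's only power statement is one sentence in 9.2, which also appears in 5.5: "A sample size of at least 100 students in each group was determined to have a power of .8 to .9". The effects listed are a difference in proportions of at least 20%, "Chi-square values of five or more with one or two degrees of freedom", and "mean differences of at least 0.3, and odds ratios greater than three in logistic regression". The sentence does not tie any effect to an endpoint.

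The tests are given elsewhere. For kit requests and kit returns, 9.4.2 says: "We will use a directional Z test for difference in proportions". For knowledge, 9.4.3 says: "Differences in radon knowledge between the two groups will be tested with directional, independent t-tests". Regression and chi-square tests appear only in 9.4.7, which describes a covariate-adjusted model with interactions and adds that "significant interactions will be described by levels of univariate Z or chi-square tests". Section 9.4.1 refers to Type I error but sets no level.

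The only rates in the document are in 2.2. In the pilot, 24% of app users ordered a kit and 9% completed a test, after one month of use and with no control group. Section 9.2 does not use these rates.

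**The concern.** A power figure needs an alpha, an effect on a defined scale, and a variance or base rate. The sentence gives the sample size, a power range and four bare effect sizes. Because the primary and knowledge tests are already directional, the main item missing for them is alpha. For 0.3 the unit is also missing, and for the odds ratio the brochure rate.

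A chi-square of five is a further problem. Power is computed for an effect, and a chi-square value is an effect measure only if it is meant as a noncentrality.

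At stake is how a null result is read. A reader who takes .8 to .9 as covering every endpoint would give a non-significant knowledge or kit-return result more weight than the design supports. Knowledge also depends on the post-exposure survey. Section 7.3 foresees non-completion ("A participant will be considered lost to follow-up if he or she fails to complete the post-exposure survey") and 5.5 describes a reminder ("Participants who did not complete the post-exposure survey two weeks after the initial email received a reminder email"), but 9.2 makes no allowance for it.

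**Working it through.** **Inputs from the document:** 100 per arm, power .8 to .9 and the four effects (9.2); directional Z test and directional independent t-test (9.4.2, 9.4.3); pilot rates of 24% and 9% (2.2). **Assumed:** alpha of 5%, one-sided for the directional tests, with two-sided results alongside. All figures take 100 analysed per arm unless stated.

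**1. Difference of 20 points (the part that reproduces).** The pooled Z test rejects when (pA − pB)/√(2p̄(1 − p̄)/100) > 1.645. Power is lowest at 60% v 40%. The normal approximation there is Φ[(0.20 − 1.645 × 0.0707)/0.0693] = Φ(1.208) = 0.886. Exact binomial enumeration gives 0.890 one-sided and 0.826 two-sided, and these are the minima over brochure rates of 0–80% in 1-point steps. A 20-point advantage is possible only if the app-arm rate is at least 20%. At the pilot's 24% it means a brochure rate of 4% or lower.

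**2. Mean difference of 0.3.** If the unit is SDs of the analysed score, the noncentrality is 0.3 × √(100/2) = 2.121 with 198 df.
- Power is 0.681 at one-sided 5% and 0.560 at two-sided 5%.
- Solving for the detectable difference gives 0.353 (80%) and 0.415 (90%) one-sided, and 0.398 and 0.461 two-sided.
- With 90, 85 or 80 analysed per arm (assumed), one-sided power at 0.3 is 0.641, 0.619 or 0.597.

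Readings that the plan does not state give other results:
- One-sided 10%: 0.798.
- Raw-score SDs with change scores, d = 0.3/√(2(1 − r)): 0.80 at a pre-post correlation r of about 0.64, and more above it.
- A within-group t-test with n = 100, which is not the planned test: 0.909 one-sided, 0.844 two-sided.
- 0.3 items on the 20-item score, at assumed SDs of 2, 3 and 4 items: 0.278, 0.174 and 0.132.

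**3. Chi-square of 5.**
- As a noncentrality at 5%: 0.609 (1 df) and 0.504 (2 df). A directional 1-df version gives Φ(√5 − 1.645) = 0.723. Even at alpha 10%, the 2-df figure is only 0.628.
- As an observed statistic it is not an effect size. With 2 df it lies below the 5% critical value of 5.99 (p = 0.082).

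**4. Odds ratio of 3.** With brochure rate p, the app-arm rate is 3p/(1 + 2p). The figures below are exact power of the pooled Z test for a group effect without covariates.

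| Brochure rate | App-arm rate | One-sided 5% | Two-sided 5% |
|---|---|---|---|
| 3% | 8.5% | 0.541 | 0.377 |
| 5% | 13.6% | 0.699 | 0.578 |
| 8% | 20.7% | 0.834 | 0.745 |
| 10% | 25.0% | 0.885 | 0.816 |
| 75% | 90.0% | 0.885 | 0.816 |
| 80% | 92.3% | 0.823 | 0.732 |

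Power is at least 80% for brochure rates of about 8–80% one-sided and about 10–75% two-sided.

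**5. The primary endpoints at the pilot's rates (scenarios only).** One-sided 5%, exact power of the Z test:
- Requests, app arm 24%: 80% power needs a brochure rate of about 10.8% or lower (0.802).
- Returns, app arm 9%: 0.804 against a brochure rate of 1.7%, 0.788 against 1.8% and 0.756 against 2.0%. So 80% needs roughly 2% or lower, strictly a little below 2%.

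**The case against.** The strongest reply is that no figure in 9.2 has been shown to be miscalculated. Each shortfall rests on an assumed alpha and an assumed meaning. Some readings do bring 0.3 to about 80%, and one is not remote: change in knowledge is the stated endpoint, so 0.3 could be in raw-score SDs with a pre-post correlation of 0.64 or more. This stands to the extent that 68% must be given as conditional. It does not rescue the sentence, because none of these readings is stated. Nor does it help the chi-square claim, which falls short for both 1 and 2 df even at alpha 10%.

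Second, the effect that matches the primary test holds. That is correct, and the claim should be kept.

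Third, 9.4.1 and 9.4.2 already promise confidence intervals and absolute and relative differences, which are the main tools for reading a null result. That limits the harm but does not make the power statement right.

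Fourth, 100 per group is a floor, recruited from roughly 800 enrolled students a semester (5.5), and the document gives no attrition rate. The 90, 85 and 80 scenarios are therefore illustrations only.

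Fifth, the odds-ratio range is for an unadjusted group effect, whereas 9.4.7 describes a covariate-adjusted model that it does not call directional. Any retained range must therefore state its model and sidedness.

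Sixth, at low rates the pooled Z test is not exact. When both arms are at 3% its true one-sided size is about 6.2%, so the kit-return threshold should be given only roughly.

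**Conclusion.** The concern holds. The joint claim cannot be verified from the document, and at a conventional 5% level it fails as a whole for the planned tests. The 20-point part is sound at 89% or more one-sided and 83% or more two-sided, given an app-arm rate of at least 20%. The 0.3 part gives 68% one-sided or 56% two-sided if it is in SDs of the analysed score. The chi-square part gives 50–61% as a noncentrality. The odds-ratio part holds only over a limited range of brochure rates. All of this rests on an assumed alpha of 5% and 100 analysed per arm.

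A reader might infer that 100 per group is too few, or that the trial is underpowered for kit return. The document supports neither. The claim that matches the primary Z test holds. The pilot's 9% comes from one month of app use without a comparison group, so it is a scenario and not a planning rate. What can be said is that the 20-point claim gives no assurance for kit return if the app-arm rate is near that figure. Nor can one conclude that the 0.3 was computed wrongly, since its unit is unknown.

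This should be fixed. It concerns how the results are read, not how the trial is run.

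**What to change.** Reword 9.2 and 5.5, leaving sample size, tests and analysis sets unchanged. If recruitment is complete, as the past tense in parts of 1.1 and 5.5 suggests, label the figures as restated and not as the original basis for the sample size.

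- **Alpha and primary test.** State alpha for the directional tests. Keep the 20-point claim as the basis for the Z test, and add that it needs an app-arm rate of at least 20%.
- **Knowledge.** Replace the 0.3 with a detectable standardised difference of 0.35–0.42 for 80–90% power at one-sided 5% with 100 analysed per arm (0.40–0.46 two-sided). Name the analysed score (change or 3-month), and say that power is lower if post-exposure surveys are missing.
- **Chi-square.** Delete the claim.
- **Odds ratio.** Delete the claim, or limit it to a group effect without covariates or interactions and state its sidedness: 80% power for brochure rates of about 8–80% at one-sided 5%, or about 10–75% at two-sided 5%.
- **Kit return.** State that power depends on a base rate the plan does not give. As an example, with 9% in the app arm, 80% one-sided power needs a brochure rate of roughly 2% or lower.

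The cost is wording only, with no extra participants. The downside is that stated power becomes less favourable for knowledge and kit return.
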